**B) Neuropsychological Assessments (Specific Aim #2, see Appendix 6c for assessment samples)**

Attention, memory, executive functioning and depression are commonly disrupted following TBI and for some, these impairments persist as part of a post concussive syndrome [52]. There is evidence to suggest that rTMS has resulted in benefits in these same cognitive domains [11]. The tests in the assessment battery were selected with several factors in mind: (a) validity and reliability; (b) relevance to the literature and prior experience with these tests in previous studies of rTMS; (c) limiting the length of the battery to reduce fatigue and facilitate compliance; (d) targeting measurement of neurocognitive functions commonly found to be impaired in patients with TBI. Details regarding the following measures are provided in Appendix 6c.

**I). Cognition:** (a) Attention: Conner's Continuous Performance Test (CPT II) [4; 58] and added Eye-Tracker assessment. (b) Memory: Hopkins Verbal Learning Test[16; 36; 73]; (c) Executive Functioning: Trail Making Test A and B; Stroop Test ;

**II). Mood:** Hamilton Rating Scale for Depression (HRSD) [1; 6; 65];

**III). Quality of Life:** SF-36;

**IV). PTSD (only at Visit 2):** Clinician-Administered PTSD Scale (CAPS); and

**IV). Global Pain:** Brief Pain Inventory (BPI)

The duration of all neuropsychological/behavioral tests is estimated to be less than 2 hours 45 minutes. The duration of the assessment appears to be reasonable and non-excessive for the patients based on the investigators' previous experience. However, if the subjects are unable to complete all the assessments in one setting, they will be asked to return in the following day to complete the assessment.

**C) Other study associated assessments consist of:**

**1) Weekly Phone Assessment:** After the post-treatment one-week assessment, the study coordinator will conduct weekly phone contacts with the subjects for pain and side effect assessments until the completion of the study. The study coordinator will also trouble shoot any potential issues that may lead to unnecessary subject dropout with the assistance of the PI;

**2) Side Effect Assessment:** During each study related visit (after Visit 2) and weekly phone assessment, side effect assessment will be conducted to monitor any study related complication. Patient will be asked to report any

potential neurological side effect such as soreness at the side of the treatment, dizziness, or increase of pain related to the treatment. Investigators will determine whether these side effects are study or non-study related and report to the Institutional Human Subject Protection Committee, VA Research and Development Committee and the study Data Safety Monitoring Board according to the protocol; and

3) **Concomitant Medication:** Any medication that a subject uses during the study is considered concomitant medication. This includes prescription and non-prescription treatment such as contraceptives, vitamins, topical preparations, herbal preparations, and non-pharmacological therapies. Concomitant medication information (please see Human Subject for allowable and prohibited concomitant medications during the study) will be collected for all subjects during the screening, treatment, between visits (recorded in the Daily Headache Log) and subsequent post treatment visits. Information regarding subjects' previous failed treatments will also be collected at the screening visit. Subjects will be instructed not to alter medication regimens during the study without consultation with the investigators.

## D) Functional imaging

Resting state functional imaging of the brain will be obtained after (within 72 hours) Visits 2 and 13. To minimize medication related interference, patients will be asked not to take any headache related rescue medications 24 hours prior to the scanning. Head movement during scanning will be minimized by instructing the subjects to hold their head still during the scanning, applying padding between the subjects' head and the head coil, and having subjects wear a cervical collar to minimize both lateral and axial head movements [40; 69]. 5-minute resting fMRI data will be collected via a 1.5T GE scanner with T2\*- weighted EPI-sequence (TE=30 ms, TR=2.0s, a=90°, TH=4mm, 32 slices, FOV=220x220 mm^2, MA=64x64.

Evoked Heat pain state fMRI will be conducted according to a well established protocol[79-81] (See Appendices 3B&3C). During the scan, an intermittent thermal heat pain stimulation will be delivered via a thermode controlled by a computer at the left calf area in 15 second pulse rates for about 10 minutes. The equipment used is called a quantitative sensory threshold (QST) and has been used in several previous studies.

To be consistent with the stimulation site in the study, the location for the evoked heat pain measurement was marked at the medial aspect of the left calf between the 6th and 7th marking of an elastic band which consisted of a total of 13 increments, extending from the medial malleolus to the medial tibial plateau. This method of peripheral sensory testing has been well established in literature and has been used extensively in pain-related studies [74-78]. The subjects are then asked to rate the intensity of HP on a M-VAS.

## **E) Study intervention**

Prior to study intervention (within 72 hours of Visit 2), brain anatomical scans will be obtained with rapid gradient-echo (MP RAGE) sampling (176 slices T1, 256x256 and 1cm slice thickness) in GE 3.0 MRI scanner. The images will then be processed by ANT Visor2-XT software for the neuronavigation guided rTMS treatments according to the following protocol:

**I). Preparation:** The patients will be asked to sit in a comfortable chair and relax as much as possible. Electromyography (EMG) recordings from the contralateral abductor digit minimi (ADM) muscle will be acquired with silver-silver chloride surface electrodes, using a muscle belly-tendon set-up, with a 3cm diameter ground electrode placed at the wrist. Manufacturer pre-installed software will be used to collect signal with a recording time window of 200ms. TMS will be performed with a figure-of-eight coil connected to MagPro B65 (Alpine BioMed, Fountain Valley, CA). Before beginning a rTMS session, subjects will be asked to sit in the study intervention chair with the rTMS coil positioned on their head, keeping their head as still as possible for 3.5 minutes. This is to acclimate the patients to the study intervention set-up prior to initiating the intervention.

## **II). TMS Neuronavigation System**

All patients' brain anatomical MRI will be obtained and examined by [name], Chief of Neuroradiology. The acquired scans will then be processed by the ANT Visor 2-XT Software. During TMS Neuronavigation, stereotaxic data for the localization of the TMS stimulation site are recorded and will allow the investigators to visualize the TMS coil and focus the magnetic flux onto the target region. The three fiducial points (nasion, left and right perauricular), treatment location will be marked onto the patients' cortical image so that the location of each treatment and distance between the center for the coil and target region will remain the same for each treatment session. This approach will account for the variability of location between subjects and treatments, which may arise without the neuronavigation guidance.

## **III). Determination of resting motor threshold**

This assessment will be conducted at the first (Visit 3) and the last (Visit 12) treatment session. A constant suprathreshold stimulus intensity will be applied via a figure-of-eight coil, which will be moved under the guidance of TMS Neuronavigation over the left motor cortex (Brodmann Area 4). Once the optimal location is visually identified, a single pulse TMS will be delivered to that location starting at the suprathreshold intensity and decreasing in steps of 2 % of the stimulator output. The resting motor threshold (RMT) will be defined as the minimal intensity required to elicit motor evoked potentials of 50 V peak to peak amplitude in five out of 10 consecutive trials [30]. The location of the cortex used for the establishment of the RMT will be marked on the neuronavigational software and used for subsequent treatments. The distance between the center of the probe and the target site will be recorded as well.

## **IV). Active/Sham-rTMS at left MC**

Active or sham rTMS will be delivered via the MagVenture Cool-B65 Active /Placebo coil which performs as a coil with both active (A) and placebo (P) functions. This is an ideal coil for double-blinded clinical studies requiring a very high number of stimuli. It consists of a built-in orientation software controlled by the randomization code , which determines which side of the coil should be placed towards the subject. The coil symmetrical design with no indication of active vs. placebo sides makes it ideal for double-blinded studies. This coil with the projection of live neuronavigation guidance images and noise generator addresses several pertinent blinding parameters related to rTMS clinical trials by providing: 1) the auditory click of coil discharge; 2) the visual stimulation including the coil location and orientation; 3) the tactile sensation of coil tapping or scalp muscle activation; and 4) no direct brain stimulation when the placebo coil is faced towards the targeted brain region. The treatment site for the left MC will be the same as the site where the RMT is determined. The stimulation target will be marked on cortical surface using the ANT Neuronavigation System, which is compatible with the Cool B65 A/P coil. The marked location will be used for all subsequent treatments. Active-rTMS consists of 20 trains with each train containing 100 pulses delivered at 10 Hz and 80% RMT stimulation intensity over the area as determined above. A total of 2,000 pulses will be delivered at each area over 3 to 4 minutes. This treatment protocol is within the treatment safety guideline recommended by the FDA and the PI has been using this protocol for over six years with good clinical outcome and minimal side effects [74].

## **VI). Process of randomization and treatment double blinding**

The un-blinded study biostatistician, [name], will create a list of patient identification numbers with randomized treatment assignments (A = Active/Real, B = Sham) using the SPSS software prior to the start of the study subject recruitment. Blocked randomization will be used with random block size of 3 or 6. Separate lists (up to 12) of replacement patient identification numbers will also be created so that replacement patients are assigned the same treatment as patients they are replacing. Patients will be randomized to study treatment groups in a 1:1 ratio. [name] will be contacted by the study coordinator with subjects' unique master ID number (sequential number, independent from any protected health information or any other identification source) and their descriptive information. After a subject signs the study consent, the study coordinator will be provided with that subject's randomization code. A minimization random assignment procedure will be used to match subjects on four variables: 1) mechanisms of injury; 2) gender; 3) severity of headache, and 4) past failed therapies for their headache. The minimization random assignment procedure aims to obtain equal numbers of subjects at the different levels of each matching variable. In contrast to stratified randomization, which aims for equal numbers of subjects in each treatment for every possible combination of the interested variables, the minimization method restricts its aim to equalizing treatment numbers at the different levels of each variable taken separately [20; 77]. Essential for this study, the procedure allows sequential assignment of subjects. This method has been shown to be superior to both simple and

stratified randomization in producing a balance for separate prognostic variables, particularly when the number of strata is large in comparison with the number of subjects. In addition to violations of inclusion and exclusion criteria, reasons for randomization failure include major protocol deviation, lost to follow-up, voluntary withdrawal, and study termination will be communicated with [name]. The randomization code will be input into the TMS software in guiding the orientation of the Cool B65 A/P coil for each subject based on a built-in gravity sensor mechanism. This method of double blinding with the use of Cool B65 A/P coil as recommended in a recent guideline for rTMS in pain/headache related studies [32] will blind both the subjects and the investigators to the study treatments.

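### The randomisation section gives allocation rules that cannot all hold (blocks of 3 at 1:1, an advance list, sequential minimization, same-arm replacement); separately, the maxT resampling rule is not stated

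*Combined protocol and SAP*

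**What the plan says.** All of the following is current text in Section 9, under *VI). Process of randomization and treatment double blinding*, unless another heading is named.

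- **Blocks and ratio.** "Blocked randomization will be used with random block size of 3 or 6", and "Patients will be randomized to study treatment groups in a 1:1 ratio". The hypothesis 1 analysis lists two treatment groups.
- **Advance list.** The biostatistician creates identification numbers with assignments "using the SPSS software prior to the start of the study subject recruitment". *E) Blinding Strategy and Assessment* again refers to a randomization list.
- **Minimization.** "A minimization random assignment procedure will be used to match subjects on four variables": injury mechanism, gender, headache severity and past failed therapies. "Essential for this study, the procedure allows sequential assignment of subjects".
- **Stratification.** The section sets minimization apart from stratification: "In contrast to stratified randomization, which aims for equal numbers of subjects in each treatment for every possible combination of the interested variables". *Research Design* nevertheless says that randomised patients are stratified on injury mechanism and headache severity, and then names the same four variables.
- **Replacement.** Separate lists (up to 12) are prepared so that "replacement patients are assigned the same treatment as patients they are replacing".
- **Code release.** The coordinator sends the biostatistician the subject's ID and descriptive information. "After a subject signs the study consent, the study coordinator will be provided with that subject's randomization code".

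*Data Management, Analysis and Power Calculations* and *Statistical Analysis* control family-wise error at 0.05 with the Westfall-Young randomization maxT procedure. Neither says how arm labels are resampled.

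**The concern.** An allocation rule has to be definite enough for someone else to check that each subject received the assignment the rule produces. Here three mechanisms compete. A fixed list ignores the characteristics of those already enrolled, whereas minimization depends on them, so a list made before recruitment cannot contain minimized assignments. Inherited arms come from neither mechanism.

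Two things are at stake. The first is whether the allocation can be checked against the protocol, including how replaced and replacement subjects are handled. The second is the reference distribution for the multiplicity correction. A procedure that re-randomises subjects to arms gives p-values that depend on the scheme replayed, and schemes that balance prognostic factors differ from schemes that do not.

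**Working it through.** **1. Block arithmetic.** With two arms, a block of 6 gives 6/2 = 3 per arm. A block of 3 gives 3/2 = 1.5 per arm, so every such block splits 2:1 or 1:2. The text does not say which arm takes the extra patient.

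**2. Arm sizes if the blocked list governs.** Assume that sizes 3 and 6 are equally likely.

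- Extra patient to either arm at random: 20,000 simulated lists of 128 give a mean of 64.0 per arm, SD 1.96 and a 95% range of 60 to 68.
- Extra patient always to the same arm: that arm gets (2 + 3)/(3 + 6) = 0.556 of patients, or 0.556 × 128 ≈ 71 against 57. Nothing in the text says this is intended.

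**3. Power.** The plan states 85% power with 128 patients for a difference rising to 0.5 SD at the last time point. That figure can be neither confirmed nor refuted, because the correlation and covariance structure behind it are not given. A linear-trend calculation with six time points, compound symmetry and 20% attrition gives about 70% at correlation 0.2, 87–88% at 0.5 and above 99% at 0.8. It is not in dispute here. To isolate the effect of unequal arms, take a simple two-group comparison at 0.5 SD, two-sided 5%, before dropout:

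power = Φ(0.5 × √(n₁n₂/(n₁+n₂)) − 1.96)

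| Split | n₁n₂/(n₁+n₂) | 0.5 × √ | Power |
|---|---|---|---|
| 64:64 | 32.00 | 2.828 | 80.7% |
| 60:68 | 31.88 | 2.823 | 80.6% |
| 71:57 | 31.62 | 2.811 | 80.3% |

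**4. Which mechanism assigns?** A ready-made, unstratified list needs no patient characteristics; minimization does. The biostatistician receives descriptive information, the section argues for minimization at length, and it calls sequential assignment essential. These point to minimization. Against them stand the block sizes, the list made before recruitment and the later reference to a list. No sentence says how they combine.

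**5. Effect of replaying a different scheme.** Let R² be the share of outcome variance explained by the four factors. The documents give no value, so 10% and 30% are assumptions. If minimization balanced the factors perfectly, the variance of an unadjusted difference in means would shrink by the factor 1 − R². A replay that ignores this has approximate size 2Φ(−1.96/√(1−R²)):

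- R² = 0.1: 2Φ(−2.066) = 3.9%
- R² = 0.3: 2Φ(−2.343) = 1.9%

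Real minimization balances less than perfectly, so the true values should lie a little closer to 5%. The simulation used 8,000 trials of 128 with 499 re-randomisations each (Monte Carlo SE about 0.25 points). It assumed factor levels of 2, 2 (85/15), 3 and 2, allocation probability 0.8 and one normal outcome:

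| Assigned / replayed, unadjusted | R² = 0 | R² = 0.1 | R² = 0.3 |
|---|---|---|---|
| Minimization / blocked | 5.3% | 4.2% | 2.4% |
| Blocked / minimization | 5.1% | 6.3% | 9.4% |

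Matching schemes gave 4.9–5.2%. Adjusting for the four factors gave 4.8–5.5% whichever scheme was replayed. In the first row, power at 0.5 SD was 80.9% instead of 83.3% (R² = 0.1) and 83.4% instead of 90.1% (R² = 0.3).

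A separate simulation used maxT over six outcomes (assumed correlation 0.5), with minimization assigned and plain label permutation replayed. Family-wise error was 4.8%, 3.7% and 1.4% at R² of 0, 20% and 40%. Replaying minimization instead gave 4.5–6.3% (Monte Carlo SE about 0.6 points).

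**The case against.** The strongest reply is that minimization is plainly the working method and the rest is leftover wording: the list might serve only as its random element or tie-breaker. That reading is plausible, and the workflow supports it, but it is an inference. It also leaves the block sizes and the inherited arms unexplained.

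Several further objections stand in full or in part:

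- **A reader might infer that the allocation conflict leaves the Westfall-Young procedure undefined or unusable.** It does not follow. The resampling rule would be unstated even under one clear scheme, and a plain label permutation could still be run under exchangeability. The two gaps are separate.
- **A reader might infer inflated type I error from the 6.3% and 9.4%.** Those need the blocked list to have assigned patients and minimization to be replayed. Nothing in the text makes that pairing likely.
- **The simulations are not the planned analysis.** They use unadjusted differences in means. The plan is a mixed model with saturated treatment-by-time terms and baseline among the repeated measures. A stable effect of a factor on headache level largely cancels in a treatment-by-time contrast, so distortion remains only so far as the factors predict change.
- **A reader might infer that concealment is lost for replacements.** That would need someone to guess the replaced patient's arm and know the pairing. Coordinator and investigators are blinded, and no text gives site staff the pairing.
- **Dropouts are not discarded.** *Statistical Analysis* keeps them in the model. What stays open is the trigger for replacement. Loss to follow-up and withdrawal are listed as randomization failures reported to the biostatistician, but they are not named as triggers. Whether the 12 counts lists or patients is also unclear.
- **Code release on consent** does not show that ineligible subjects are randomised: *Research Design* limits randomisation to those meeting the enrollment criteria.

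**Conclusion.** The contradiction stands and should be corrected. Blocks of 3 cannot be 1:1 between two arms, a list made before recruitment cannot carry out minimization, and inherited arms belong to neither scheme. The text leans towards minimization without saying so.

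The numerical consequences are modest. The effect on arm sizes and power is negligible if the odd patient in a block of 3 is placed at random. On the more likely reading, the risk from an unstated resampling rule is a conservative test and some lost power, in proportion to how far the four factors predict the analysed contrast. The 4.2% and 2.4% illustrate this for an unadjusted difference in means; they rest on assumed R² values, factor levels and allocation probability, and the planned model may show less. Confidence is high for the textual conflict and low for any particular error rate in the planned analysis.

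**What to change.** The COVID-19 sections show that subjects are already enrolled, so the order matters.

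1. Confirm from the biostatistician's records which method has assigned subjects so far.
2. Keep one method in *Research Design* and in the randomisation section: either minimization on the four factors with a stated random element, or permuted blocks of even size. Delete blocks of 3 and the conflicting descriptions, including stratification on two factors. If the method in use has to change, record the date.
3. Drop same-arm replacement; any added subject takes the next regular assignment. Analyse every randomised subject, replaced and replacement alike, in the assigned arm.
4. As the main statistical safeguard, adjust the primary mixed model for the four balancing factors, including their interactions with time. At present the plan says only that such adjustment is possible.
5. State that the maxT resampling replays the scheme actually used, by period if it changed.

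The cost is a check of records, an amendment of wording, minor reprogramming and a few model degrees of freedom. Completers would no longer be topped up by arm. No patients, visits or procedures are added.

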## **E) Blinding Strategy and Assessment**

In addition to the double blinding A/P coil, several blinding strategies will be applied to minimize biases in the study: 1) All subjects are allowed to visualize the TMS coil over the cortical treatment sites on a projected screen and hear the clicking noise during either active or sham rTMS; 2) Standard instruction before and after each rTMS treatment will be given to each subject to minimize instructional related study biases; 3) The procedure for determining the RMT will be identical for each subject. To ensure adequate blinding throughout the study, all subjects will be surveyed whether they receive active-rTMS (Groups A) vs. sham-rTMS (Group B) at Visits 5, 8 and 14; and 4) To minimize investigators' bias, the study coordinator responsible for assessment will go through extensive training by the study PI prior to enrollment of any subjects on both the protocol and administration of assessments. The inter-rater reliability (an intra-class correlation coefficient of  $\geq 0.90$ ) between the study coordinator and the gold standard will be established by the PI. This reliability will be monitored every six months by study statistician, [name]. Both the study coordinator and the investigators will be blinded to the treatment given to the subject. The randomization list will be provided by the study biostatistician. In addition, all data collected will be organized and sent directly to the biostatistician for analysis without going through the PI or any other investigators.

